7.1.5 Subject Selection (including control group selection if necessary)

(1) Inclusion Criteria

Patients must meet all the following inclusion criteria to qualify for enrollment:

- 1) Age 18 to 75 years old, gender-unrestricted, non-pregnant female;
- 2) Understand and be willing to sign an informed consent form;
- 3) Diagnosed with coronary heart disease;

- 4) Intrusive ICA and FFR measurement are needed;
- 5) Visual coronary angiography showed at least one moderate stenosis lesion (diameter stenosis of 30% - 70%) on the coronary artery with diameter $\geq 2.5\text{mm}$

(2) Exclusion Criteria

Patients meet any of the following criteria is not qualified for enrollment:

- 1) Patient who do not understand or are unwilling to sign an informed consent form;
- 2) Has a history of myocardial infarction;
- 3) Patient with other serious diseases are not suitable for clinical trials, such as a complex congenital heart disease history, severe heart failure (NYHA cardiac function level IV), long QT syndrome, severe hypertension, Severe asthma, severe chronic obstructive pulmonary disease, liver and kidney dysfunction and other serious infections and critical illnesses;
- 4) Coronary intervention surgery contraindications;
- 5) Patient with ATP contraindications (ATP contraindications: sinus syndrome, sinus insufficiency and the elderly with cautious use or no use);
- 6) The clinical manifestations of patients show acute instability, including acute chest pain (sudden appearance), cardiogenic shock, unstable blood pressure (systolic pressure less than 90mmHg), severe congestive heart failure or acute pulmonary edema;
- 7) The angiography shown or suspect of thrombosis;
- 8) The angiography shown or suspect of dissection;
- 9) Left main coronary artery disease, target blood vessels with severe curvature or calcification lesions, total occlusion;
- 10) There are any other factors that the investigator considers unsuitable for inclusion or completion of this study.

(3) Standards and procedures for terminating trial / trial treatment

Subject may withdraw from the trial at any time during the trial without any reason; and after signing of the informed consent form, subject can still choice not to participate in any trial procedures (by doing so it's equivalent to withdraw the consent). If after signing the informed consent form, the subject chooses not to participate in the trial, investigator must be informed. But no matter what happens, the subject has the right to continue to receive other standard treatments.

The investigators can also withdraw subjects from the trial based on medical judgment at any time.

1) Criteria for the subject to be withdrawn from the trial:

The subject meets any of the following and trial stops:

- The subject withdrew his/her informed consent
- The investigator believes that there are any safety reasons (adverse events or serious adverse events)
- The investigators believe that subject has poor compliance with trial protocol

2) Criteria for terminating the trial:

- Sponsor requests to terminate the trial
- The regulator or the relevant department of the administration requests the termination of the trial
- For the purpose of protecting subject rights and interests, the investigators believe that the subject should terminate the trial
- Subject death

3) Elimination Criteria:

- After enrollment, subject found to not meet the inclusion criteria, or meet exclusion criteria
- Serious breach of protocol (confirmed by the principal investigator).

(4) Enrollment Time

Before the selection, subject's consent and signed informed consent form required

- 1) Subject's general information, past medical and disease history, examination of combined drug use
- 2) Physical examination, vital signs, clinical diagnosis
- 3) After coronary angiography, the investigators combined with angiographic images and subject inclusion/exclusion criteria to determine whether to use the control device and the investigational device to determine identified lesion's FFR, if the

inclusion criteria are met, and no exclusion criteria are met, subject will then be selected for the trial and the time will be recorded for enrollment.

(5) The Expected Overall Duration of Clinical Trial and Rational

The overall duration of clinical trial, including the time of signing clinical trial agreement in all trial hospitals, ethical committee approval and post-conference rectification, filing time, trial initiation, patient enrollment, and FFR procedure time, collection, statistics, and summary of trial data, report creation time, etc., is expected to be 2 years.

(6) The expected duration of each subject's participation

Considering that the time of enrollment and the operation time are the same day, the subjects are required to complete the informed consent form signing, vital signs, physical examination, medical history investigation, and clinical diagnosis within one week before enrollment. Each trial subject's participation time is set at the end of the visit from the time the subject signs an informed consent form, and the expected duration of each subject's participation is no more than 9 days, based on the number of visits set by the clinical trial program.

(7) Number of subjects required for clinical trials

A total of 300 subjects are planned for this trial. Through the results of angiographic images and inclusion/exclusion criteria, investigator will confirm if the subject met the trial requirements and those meets all the qualifications will be enrolled. After enrollment and logged into the central registration system, subject's FFR measurements were performed using a control device after the investigational device to assess the Fractional Flow Reserve of the coronary artery stenosis

7.1.6 Effectiveness evaluation methods

7.1.6.1 Description of effectiveness parameters

(1) Primary effectiveness endpoint:

Diagnostic consistency rate in the diagnosis of coronary heart disease with investigational device and control devices: Each subject will be considered as a research unit (for patients with multiple lesions, the method of converting the results of multiple lesions into patient level is defined in the statistical analysis plan), and the coronary artery FFR_{PW} measured by control device will be taken as reference, when the measurement of control device is

positive ($FFR_{PW} \leq 0.80$) or negative ($FFR_{PW} > 0.80$), the investigational device is also positive or negative.

(2) Secondary effectiveness endpoint

- The sensitivity and specificity of the investigational device used to diagnose coronary heart disease: Taking the subject as the research unit, the sensitivity and specificity of investigational device for diagnosis of coronary heart disease will be calculated. FFR_{PW} of coronary artery measured by control device will be used as the reference and $FFR_{PW} \leq 0.80$ as positive threshold.
- Positive predictive value, negative predictive value and area under working characteristic curve: Taking subjects as research units, FFR_{PW} measured by control device as reference, and $FFR_{PW} < 0.80$ as positive threshold, the positive predictive value, negative predictive value and area under ROC curve (AUC) of investigational device for diagnosis of coronary heart disease will be calculated.
- Passing-Bablok Regression Analysis: Taking the blood vessel as the research unit, Passing-Bablok regression analysis will be used to analyze the FFR_{WS} value of coronary artery measured by the investigational device and the FFR_{PW} value of coronary artery measured by the control device.
- Bland-Altman Deviation Analysis: Taking the blood vessel as the research unit, Bland-Altman deviation analysis will be used to analyze the FFR_{WS} value of coronary artery measured by the investigational device and the FFR_{PW} value of coronary artery measured by the control device.
- Pearson linear correlation analysis: Taking the blood vessel as the research unit, Pearson linear correlation analysis will be used to analyze the FFR_{WS} value of coronary artery measured by the investigational device and the FFR_{PW} value of coronary artery measured by the control device.
- Device success rate: Taking the blood vessel as the research unit, effective FFR_{WS} and FFR_{PW} readings will be used as the criteria to judge the success rate of the devices, and the success rate of the investigational device and the control device will be compared.

7.1.6.2 Methods and time selection for evaluating, documenting and analyzing effectiveness parameters

(1) Primary effectiveness endpoint: the consistency rate in the diagnosis of coronary heart disease with investigational device and control device.

At Visit 2(FFR-ICA examination), record coronary artery FFR_{WS} measured by investigational device and coronary artery FFR_{PW} measured by control device. After all subjects completed the Visit 2, taking the subject as the research unit, the consistency

rate of investigational device for diagnosis of coronary heart disease will be calculated based on FFR_{WS} measured by investigational device. FFR_{PW} of coronary artery measured by control device will be used as the reference and $FFR_{PW} \leq 0.80$ as positive threshold.

Diagnostic consistency rate = (true positive + true negative) / (positive + negative);

Positive and negative respectively correspond to the results of the control device assay (positive when $FFR_{PW} \leq 0.80$, negative when $FFR_{PW} > 0.80$), true positive refers to that when investigational device is also positive at the same time as control device is positive ($FFR_{PW} \leq 0.80$ and $FFR_{WS} \leq 0.80$, true negative refers to that when control device is negative and investigational device is also negative ($FFR_{PW} > 0.80$ and $FFR_{WS} > 0.80$).

(2) Secondary effectiveness endpoint:

➤ Sensitivity and specificity of investigational device in the diagnosis of coronary heart disease:

At Visit 2 (FFR-ICA examination), record the coronary artery FFR_{WS} measured by investigational device and the coronary artery FFR_{PW} measured by control device. After all subjects completed the visit 2, taking the subject as the research unit, the sensitivity and specificity of investigational device for diagnosis of coronary heart disease will be calculated based on FFR_{WS} measured by investigational device. FFR_{PW} of coronary artery measured by control device will be used as the reference and $FFR_{PW} \leq 0.80$ as positive threshold.

Sensitivity = True Positive / Positive;

Specificity = True Negative / Negative;

➤ Positive predictive value, negative predictive value and area under the working characteristic curve in the diagnosis of coronary heart disease with investigational device:

At Visit 2 (FFR-ICA examination), record the coronary artery FFR_{WS} measured by investigational device and the coronary artery FFR_{PW} measured by control device. After all subjects completed the Visit 2, taking the subject as the research unit, the positive predictive value, negative predictive value and area under the working characteristic curve of investigational device for diagnosis of coronary heart disease will be calculated based on FFR_{WS} measured by investigational device. FFR_{PW} of coronary artery measured by control device will be used as the reference and $FFR_{PW} \leq 0.80$ as positive threshold.

Positive predictive value (PPV) = true positive / (true positive + false positive);

Negative predictive value (NPV) = true negative / (true negative + false negative);

ROC curve drawing and AUC calculation: In a two-dimensional coordinate map, set the horizontal x-axis to false positive rate (False Positive Rate, FPR), vertical y-axis is set to true positive (True Positive Rate, TPR). The FFR_{WS} measured by the investigational

device can be obtained from a TPR and FPR based on its performance on the test sample, adjust the diagnostic threshold for FFR_{WS} , get a series of points that are connected in turn (including (0,0) and (1,1) the two points), it is called the ROC Curve of FFR_{WS} . As the name implies, the value of the AUC is the area below the ROC curve. Curve drawing is done by using MedCalc software.

- **Passing-Bablok Regression Analysis:** After all subjects completed Visit 2 (FFR- ICA examination), taking the blood vessel as the research unit, using FFR_{WS} value of coronary artery measured by the investigational device as the vertical y-axis, and the FFR_{PW} value of coronary artery measured by the control device as the horizontal x-axis to perform Linear regression analysis and record regression analysis equation, slope and intercept.

- **Bland-Altman Bias Analysis:** After all subjects completed Visit 2 (FFR- ICA examination), taking the blood vessel as the research unit, Bland-Altman deviation analysis will be used to analyze the FFR_{WS} value of coronary artery measured by the investigational device and the FFR_{PW} value of coronary artery measured by the control device, and draw deviation map. In the two-dimensional rectangular coordinates of Bland-Altman deviation map, the horizontal x-axis of abscissa represents the average FFR of each lesion vessel measured by two devices, and the vertical y-axis of ordinate represents the difference of FFR of each lesion vessel measured by two devices.

- **Pearson Linear Correlation Analysis:** After all subjects completed Visit 2 (FFR-ICA examination), taking the blood vessel as the research unit, Pearson linear correlation analysis will be used to analyze the FFR_{WS} value of coronary artery measured by the investigational device and the FFR_{PW} value of coronary artery measured by the control device, and the correlation coefficient and P value will be recorded..

- **Device success rate:** After all subjects completed the visit 2 (FFR-ICA examination), taking the blood vessel as the research unit, use the effective FFR_{WS} and FFR_{PW} readings as the criteria for the success of the use of the device to calculate the success rate of the investigational device and the control device. Compare differences in device success rates between groups.

7.1.7 Safety Evaluation Methods

7.1.7.1 Description of Safety Parameters

The occurrence of adverse events and device defects is used as a safety

evaluation index.

7.1.7.2 Methods and Time Selection for Evaluating, Documenting, and Analyzing Safety Parameters

Adverse events were closely observed and evaluated during the screening period and in the trial. Adverse events that need to be recorded are recorded in the adverse event log. Record the time, occurrence, measures, and results of device defects.

7.2 The Trial Process

7.2.1 The Trial Process

Patients who are eligible for this clinical trial will complete screening and enrollment after Visit 1 and Visit 2, and each subject who meets the inclusion criteria and does not meet any of the exclusion criteria will undergo a series of study visits, including Visit 1 (screening period, -7-0 days), Visit 2 (FFR-ICA examination), and visit 3 (48 hours post-surgery follow up). The specific visit process is described as follows:

7.2.1.1 Visit 1 (Screening Period, -7 – 0 days)

Subject selection is according to the inclusion and exclusion criteria. This visit needs to complete the following:

1. Subjects will sign an informed consent form;
2. Demographic Information: record the subject's gender, age (date of birth), ethnicity, height, weight and other information;
3. Complete Medical History: inquire and record the subject's past illness, surgical history, current medical history, etc.;
4. Pregnancy Check-up: complete urine pregnancy test, and if positive, complete blood pregnancy test for confirmation;
5. Combined medications: record drug use that may affect device use evaluation;
6. Laboratory examination: including blood routine, liver function, kidney function, myocardial enzyme, etc.;
7. Vital signs: record subject's systolic pressure, diastolic pressure and heart rate;
8. Inclusion/Exclusion Criteria: complete the inclusion criteria item 1 to 4, and exclusion criteria item 1 to 4 and item 10;

9. Adverse Events: record adverse events that occurred during screening process.

7.2.1.2 Visit 2 (FFR - ICA examination)

On the day of the operation after the ICA examination, subjects will be selected again based on the inclusion and exclusion criteria. This visit includes:

1. Inclusion/Exclusion Criteria: complete the inclusion criteria item 5, and exclusion criteria item 5 to 9;
2. Vital signs: record subject's systolic pressure, diastolic pressure and heart rate;
3. Device information: distribute device, record device information;
4. Investigational device coronary artery FFR value: record the position of the blood vessel, record the FFR value measured by the investigational device;
5. Investigational device success rate: using effective FFR readings as a success criterion, record the success rate of the investigational device;
6. Control group device coronary artery FFR value: record the position of the blood vessel, record the FFR value measured by the control device;
7. Control group device success rate: using effective FFR readings as a success criterion, record the success rate of the control device;
8. Adverse Events: record all adverse events that occurred during subject's FFR-ICA examination;
9. Device Defects: record device defects that occurred during the use of devices;
10. Combined medications: record the combined drugs used during the trial.

7.2.1.3 Visit 3 (48 hours post-surgery follow up)

1. Laboratory examination: within 48 hours after the procedure, complete the

laboratory examination, including blood routine, liver function, kidney function, myocardial enzyme, etc.

2. Vital signs: including systolic pressure, diastolic pressure and heart rate;
3. Adverse Events: record all adverse events that occurred during subject's FFR - ICA examination;
4. Device Defects: record device defects that occurred during the use of devices;
5. Combined medications: record the combined drugs used during the trial.

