Study Device Names	Investigational device: pressure guidewire system (including wire with high-fidelity sensor strains and unique paired portable display units) Model: 100 Sponsor: Zurich Medical Inc. Agent: Shandong Visee Medical Devices Co., Ltd. Control group device: pressure guidewire Model: C12008 Manufacturer: St. Jude Medical, China Agent: St. Jude Medical (Shanghai) Co., Ltd. Registration license number: 国械注进20143775272 Analyzer Express Model: 12711 Manufacturer: St. Jude Medical, China Agent: St. Jude Medical (Shanghai) Co., Ltd. Registration license number: 国食药监械(进)字2013第3211615
Indication For Use	For patients who need coronary angiographic examination and coronary interventional treatment, pressure guidewire system is indicated to calculate the patient's blood fractional flow reserve (FFR), and to assist the physicians to make clinical decisions.

Trial Design	This clinical trial uses a multi-center, prospective, single-subject design trial method, using St. Jude Medical's pressure guidewire and Analyzer Express as a control device. The subjects who met the criteria for this study will be registered with the central registration system after enrollment. The subject's fractional flow reserve of coronary artery stenosis will first be measured using investigational device and recorded, and then measured using control device and recorded. The safety follow-up period is 48 hours.
Number of centers	Trial is expected to be held simultaneously at 5 centers in mainland China.
Sample size	300
Trial duration	The overall duration of clinical trials includes the time of signing of clinical trial site's agreements with all participating hospitals, the time of review and approval of the ethics committee meeting and the post-meeting opinion rectification, filing time, the trial kickoff, the enrollment and the subject's FFR measurement, the data collection, statistics, summary report writing time, etc., and is expected to be 2 years.
Inclusion Criteria	
 1) Age 18 to 75 years old, gender-unrestricted, non-pregnant female; 2) Understand and be willing to sign an informed consent form; 3) Diagnosed with coronary heart disease; 4) Invasive ICA and FFR measurement are needed; 5) Visual coronary angiography showed at least one moderate stenosis lesion (diameter stenosis of 30% - 70%) on the coronary artery with diameter ≥ 2.5mm

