3 OBJECTIVE AND CONTENT OF CLINICAL TRIAL

3.1 Objective

To Evaluate the effectiveness and safety of Zurich Medical's pressure guidewire system (including guidewire with high-fidelity sensors and a unique paired portable display unit), which is used to measure the coronary artery blood fractional flow reserve (FFR) to diagnose coronary heart disease, and to direct a catheter through a blood vessel. Including:

Effectiveness: Coronary artery Fractional Flow Reserve(FFR) measured by control device, St. Jude Medical's Pressure Guidewire and Analyzer Express (FFR_{pw}) will be used as a reference to evaluate FFR measured by Investigational device, the Zurich Medical pressure guidewire system (including wire with high-fidelity sensor strains and unique paired portable display units) (FFRws)'s efficacy to diagnose coronary artery disease via diagnostic consistency, sensitivity, specificity, positive predictive value, negative predictive value, and Area Under the Curve (AUC) of Receiver Operating Characteristic (ROC). Meanwhile, Passing-Bablok regression analysis, Bland-Altman deviation analysis and Pearson correlation analysis of the FFR_{pw} and FFRws will be used to evaluate the success rate of the investigational device.

Safety: The adverse events and device defects that occur during Zurich Medical's pressure guidewire system measurement of coronary arterial FFRws will be mainly evaluated.

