13.1 ADVERSE EVENTS

Definition: Adverse Events (AE), are adverse medical events that occur during clinical trials, whether or not is related to investigational devices.

Grade:

Mild: Subject can tolerate, does not affect diagnosis and treatment, do not requires special treatment, no impact on the subject's health.

Medium: Subject can not tolerate, and requires special treatment, direct impact on the subject's health.

Severe: Endangers subject's life, results in death or disability, requires emergency treatment.

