13.3 DEVICE DEFECTS

Device defects refer to under normal use of medical device presents the unreasonable risks that may endanger health and life, such as mislabeling, quality problems, malfunctions and so on.

The investigator shall record all adverse events and device defects during the clinical trial, and jointly analyze the causes of the events with sponsor, form a written analysis report includes opinions on continuing, suspending or terminating the trial, The report shall be submitted by the medical device clinical trial management department of the investigational site to its Ethics Committee for review.

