13.4 SERIOUS ADVERSE EVENT REPORTING PROCEDURES, CONTACT INFORMATION

All adverse events that occur during the clinical trials must be truthfully recorded in the adverse event table. The investigators should give targeted treatment and follow-up on adverse events until symptoms disappear or the symptoms stabilize.

In the case of serious adverse events in clinical trials, the investigator shall immediately take appropriate treatment measures on the subjects, and report in writing to the clinical investigational site's medical device clinical trial management department, and notify the sponsor in writing. The medical device clinical trial management department shall report in writing within 24 hours to the appropriate ethics committee, the competent department of food and drug supervision and administration and the health and family planning authorities of the province, autonomous region or municipality directly under the central government where the investigational site is located. In the case of a death, investigational site and investigator should provide the Ethics Committee and the sponsor with all the information they need.

For serious adverse events and device defects that potentially lead to serious adverse events, the sponsor shall report to the food and drug regulatory authority and the health and family planning authorities within 5 working days, and shall inform the other investigational sites and investigators, and through medical device clinical trial management department to inform investigational site ethics committee in a timely manner.

14 PROVISIONS ON DEVIATION FROM CLINICAL TRIAL PROTOCOL AND REVISION OF CLINICAL TRIAL PROTOCOL

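### Visit 3 limits adverse event recording to the FFR-ICA examination, which contradicts the 48-hour safety follow-up and the protocol's general recording rules

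*Combined protocol and SAP*

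**What the plan says.** Visit-level instructions (section 7.2.1):

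- Visit 1, item 9, covers adverse events arising in screening.
- Visit 2, item 8: "record all adverse events that occurred during subject's FFR-ICA examination".
- Visit 3, item 3, under the heading of the 48-hour follow-up: "record all adverse events that occurred during subject", with the FFR-ICA examination again named as the period.

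Text that sets a wider window:

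- Protocol Summary, Trial Design: "The safety follow-up period is 48 hours".
- Section 13.1 defines adverse events as "adverse medical events that occur during clinical trials, whether or not is related to investigational devices".
- Section 13.3, repeated in 20.2(14): "The investigator shall record all adverse events and device defects during the clinical trial".
- Section 13.4: "All adverse events that occur during the clinical trials must be truthfully recorded in the adverse event table".
- Section 7.1.7.2 has adverse events observed and evaluated in screening and in the trial.
- The flow chart in 7.2.2 marks the Adverse Events row at all three visits, with no limit on onset.

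Text that leans towards the narrower window: the safety objective in 3.1, repeated in 7.1.1, begins "The adverse events and device defects that occur during Zurich Medical" and goes on to the FFR measurement with that system, as what will mainly be evaluated. Section 3.2 likewise speaks of events during the measurement.

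**The concern.** The visit list assigns adverse events by when they occurred: screening at Visit 1, the examination at Visit 2. Visit 3 should take the period after the examination, but it names the examination again. Read literally, it adds no collection window to Visit 2, although it exists as a safety follow-up.

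The safety endpoint consists only of adverse events and device defects (Protocol Summary and 7.1.7.1). If some sites follow the Visit 3 item and others follow section 13, the same post-procedure event is entered at one center and not at another. Leaving out late-onset events can only lower the reported count, and the report would not show that this had happened.

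**Working it through.** No plan figure bears on this point, so the check is a comparison of texts.

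**Step 1. Is the period after the examination part of the trial?** Section 7.1.5(6) runs participation from consent to the end of the visit, for no more than 9 days. Screening takes up to 7 days (7.2.1) and the follow-up 48 hours: 7 + 48/24 = 7 + 2 = 9 days. The limit equals screening plus follow-up, so the 48 hours lie inside the trial, and rules for events during the trial apply to them.

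**Step 2. Which texts cover an event that begins after the examination and within 48 hours?**

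| Text | Covers it? |
|---|---|
| Visit 1 item 9 | No (screening) |
| Visit 2 item 8 | No (examination) |
| Visit 3 item 3 | No, as worded (examination again) |
| Flow chart, Adverse Events row | Marked at Visit 3; onset window not stated |
| 7.1.7.2 | Yes, for observation and evaluation |
| 13.1 (definition) | Yes |
| 13.3 and 20.2(14) | Yes |
| 13.4 | Yes |

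The general rules cover the event and no visit item does. That is a contradiction between two operative parts of the protocol.

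**Step 3. Could the narrow wording be read as intended?** Item 5 of the same Visit 3 list collects concomitant drugs over the whole trial, so a site could take the contrast as deliberate. The measurement wording in 3.1, 3.2 and 7.1.1 would support that. Against it, Visit 3 item 3 matches Visit 2 item 8 apart from spacing around a hyphen, which suggests carried-over text.

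**Step 4. Effect on the reported count.** Let P be the number of post-procedure events, and f the share of them arising at sites that follow Visit 3 literally. With all other events recorded alike, the shortfall is f × P. It is 0 if every site follows section 13 (f = 0) and P if every site follows Visit 3 literally (f = 1). The documents give neither P nor f, so only the direction is known.

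**Step 5. Effect on inference.** Section 8.1.2(4) describes adverse events by counts and frequencies. The only target-value test is on diagnostic accuracy (8.1.1, 8.5). No significance level, power or sample size changes.

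**The case against.** The strongest reply is that the protocol already requires these events to be recorded. Sections 13.1, 13.3, 13.4 and 20.2(14) are general and mandatory, the flow chart marks adverse events at Visit 3 without restriction, and 7.3(6) has the auditor confirm that all adverse events are recorded. On this view, item 3 is a carried-over phrase that a trained site would read past.

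Much of this stands, and it rules out stronger readings that a reader might infer:

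- *That post-procedure events fall outside the protocol's collection rules, or that the whole 48-hour window is excluded.* The general rules cover them. Only the visit instruction leaves them out.
- *That sites and the electronic case report form follow the visit list and disregard section 13.* The documents do not say so, and no form is shown.
- *That the safety objective excludes later events.* The word *mainly* in 3.1 and 7.1.1 sets emphasis and excludes nothing, and the endpoint itself carries no time limit.
- *That cardiac-marker rises would go unseen.* Visit 3 item 1 requires myocardial enzymes within 48 hours, and flow chart note 7 deals with abnormal results. Note 7 asks for review and follow-up, however, and does not say when a result is entered as an adverse event.

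The reply does not remove the contradiction. The flow chart shows that events are collected at Visit 3 but not which onset period applies, and nothing states that section 13 prevails over the visit instructions.

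**Conclusion.** The point holds as an internal contradiction. Visit 3 item 3 is narrower than the follow-up it belongs to and narrower than the general recording rules. Events after the procedure are covered by those rules but by no visit-level instruction.

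The consequence is conditional: under-recording, possibly uneven across the expected 5 centers, arises only where a site applies Visit 3 literally. The direction is downward. The size cannot be computed without an event rate and knowledge of site practice. The primary analysis is untouched. The correction is worth making because it concerns the only safety endpoint and is small.

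**What to change.** Reword Visit 3 item 3 along these lines: *record all adverse events with onset since the Visit 2 examination, through the end of the 48-hour follow-up, with time of onset*. This brings the visit into line with 13.1, 13.3 and 13.4 and adds no duty that they do not already impose, apart from stating the onset time.

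Optionally, extend the measurement wording in 3.1, 3.2 and 7.1.1 to the procedure and the 48-hour follow-up, so that objective and collection match.

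The cost is one sentence in the protocol, a check that the adverse event form holds an onset time and carries no examination-only label, and a mention in the uniform investigator training of 7.1.3. A protocol revision needs written ethics committee approval (12.2), so it can go in with any other revision. No visit, test or subject is added.
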